Tanner Scale		X										X
Vital Signs (x)	X	X	X			X	X	X	X	X	X	X
ECG	X	X(d)						X				X
Routine Laboratory Tests (e)	X	X(d)						X				X
Serum creatinine						X(w)	X(w)			X(w)	X(w)	
Bone Mineral Density		X										X
Serum(§)/Urine(*) Pregnancy Test (o)	X(§)	X(§,*)				X(*)	X(*)	X(*)		X(*)	X(*)	X(§)
ICARS (with video recording)	X(n)	X(n)						X				X
CGI-C								X				X
CGI-S	X	X						X				X
VABS		X						X				X
Quality of Life (EQ-5D-5L)		X						X				X
C-SSRS		X				X	X	X		X	X	X
A-T NEST (in selected centers)				X		X				X		
RBC osmotic resistance (t)	X	X						X				
Special Laboratory Tests (m)	X(f,g)	X(f)										X(f)
Hemolysis Panel (s)		X	X	X	X			X	X			
Genetic AT diagnosis (q)	X											
Mini-ATM detection	X						X					X
Dexamethasone PK sample		X(i)	X(i)	X(j)	X(k)	X(l)	X(l)	X(l)	X(l)	X(l)	X(l)	X(l)
EDS end product sample (u)		X				X	X	X		X	X	
Prior/Concomitant Treatments	Throughout the duration of the study											
Adverse Events	Throughout the duration of the study											

Clinical Study Protocol IEDAT-02-2015

EDS in Ataxia Telangiectasia Patients

Version 1.0, 09May2015; Version 2.1, 16Nov2015; Version 3.0 (Amend. 1), 01Feb2016; Version 3.1 (Amend. 2), 28Apr2016; Version 3.2 (Amend. 3), 25May2016; Version 4.0 (Amend. 4), 29Nov2016; Version 5.0 (Amend. 5, Site-specific), 20Sep2017; Version 6.0 (Amend. 6), 29Sep2017; Version 7.1 (Amend. 7.1), Final 13 March 2018, Version 8.0 (Amend. 8.0), Final 23 April 2018; Version 10.0 (Amend. 10), Final 16 April 2019; Version 11.0 (Amend. 11), Final 24 Jun 2020

Schedule of Visits and Assessments: 6-Month Extension Treatment Period

Visit (V) (z)	V9		V10	V11	V12		V13	V14	Unscheduled Visit (£)	V15	V16
Study Day or Month (D/M) #	M6 (b)		M7	M8	M9		M10	M11		M12(y)	Safety
Procedure (§)	Pre(c)	Post(c)			Pre(c)	Post(c)					Follow-up (p)
Informed Consent Signature	X								X		
Re-Randomization (r)	X				X						
EDS-EP Infusion (h)	7		8	9	10		11	12	#		
Culture-based sterility test (aa)		X	X	X		X	X	X	X		
Neurological Examination					X					X	
Physical Examination		X	X	X	X	X	X	X	X	X	
Tanner Scale										X	
Vital Signs (x)		X	X	X	X	X	X	X	X	X	
ECG					X					X	
Routine Laboratory Tests (e)					X					X	
Serum creatinine			X(w)	X(w)			X(w)	X(w)	X		
Bone Mineral Density										X	
Serum(\$)/Urine(*) Pregnancy Test (o)	X(*)		X(*)	X(*)	X(*)		X(*)	X(*)	X(*)	X(\$)	
ICARS (with video recording)					X					X	
CGI-C					X					X	
CGI-S					X					X	
VABS					X					X	
Quality of Life (EQ-5D-5L)					X					X	
C-SSRS			X	X	X		X	X	X	X	
A-T NEST (in selected centers)			X				X				X
RBC osmotic resistance (t)	X				X						
Special Laboratory Tests (m)										X(f)	
Hemolysis Panel (s)	X	X			X	X					
EDS end product sample (u)	X		X	X	X		X	X	X		
Prior/Concomitant Treatments	Throughout the duration of the study										
Adverse Events	Throughout the duration of the study										X

a) Efficacy evaluations on Month 6 (Visit 9) will be used as the Endpoint assessments for all efficacy measures.

Clinical Study Protocol IEDAT-02-2015

EDS in Ataxia Telangiectasia Patients

Version 1.0, 09May2015; Version 2.1, 16Nov2015; Version 3.0 (Amend. 1), 01Feb2016; Version 3.1 (Amend. 2), 28Apr2016; Version 3.2 (Amend. 3), 25May2016; Version 4.0 (Amend. 4), 29Nov2016; Version 5.0 (Amend. 5, Site-specific), 20Sep2017; Version 6.0 (Amend. 6), 29Sep2017; Version 7.1 (Amend. 7.1), Final 13 March 2018, Version 8.0 (Amend. 8.0), Final 23 April 2018; Version 10.0 (Amend. 10), Final 16 April 2019; Version 11.0 (Amend. 11), Final 24 Jun 2020

- b) Month 6 (Visit 9; Endpoint) evaluations should be performed for all patients that complete the Initial Treatment Period, as well as patients that discontinue prematurely; these evaluations will be used as the baseline assessments for the double-blind, Extension Treatment Period.
- c) Procedures to be done before (Pre) and after (Post) the EDS-EP infusion.
- d) These evaluations will be repeated only if abnormalities requiring follow-up were noted at the Screening evaluation; results from the repeat assessments must be available at baseline to confirm eligibility before the patient can be randomized to treatment.
- e) Routine laboratory assessments to include complete hematology, biochemistry, and urinalysis.
- f) Special laboratory tests include HbA1c, CD4+ lymphocytes count, α -fetoprotein (not repeated at baseline), CRP, and RBC antibodies (IgG, IgM, Qualitative Direct Coombs test – not repeated at baseline).
- g) A sample will be collected before 8:00 AM for measurement of plasma cortisol during the screening period, prior to randomization at baseline. If the basal cortisol level is within the reference normal range, the patient can be enrolled in the study. If the 8:00 AM cortisol level is below 3-5 $\mu\text{g}/\text{dL}$ (depending on assay) regardless of symptoms, or the patient exhibits signs or symptoms of adrenal insufficiency (see [Appendix 12](#)) and has a cortisol $<10 \mu\text{g}/\text{dL}$, the patient will receive a high dose ACTH stimulation test, regardless of weight, within 24 hours. If the ACTH stimulation test is normal, the patient can be enrolled after the effects of the ACTH have dissipated (e.g., 30 days after ACTH administered). If the patient fails the ACTH stimulation test they will be excluded from the study and referred to a pediatric endocrinologist, with a recommendation to prescribe stress dose steroids.
- h) Assigned study treatment: Group 1: EDS-EP dose range ~5-10 mg DSP/infusion; Group 2: EDS-EP dose range ~14-22 mg DSP/infusion; and Group 3: placebo.
- i) Samples to be collected before infusion (0 min), and 1, and 4 hr after the end of the infusion.
- j) Single sample to be collected 24 hr post-infusion (Day 2).
- k) Single blood sample to be taken in the morning.
- l) Blood samples to be collected prior to (trough) and 1 hour after (peak) the infusion, except in Months 1 (Visit 4) and Months 6 (Visit 9); only trough levels will be collected.
- m) Blood sample to be collected before 8:00 AM for measurement of plasma cortisol at the following times: (1) during the screening period (prior to randomization), (2) when patients are symptomatic, and (3) when patients are at most risk for adrenal insufficiency and adrenal crisis, such as following discontinuation or interruptions of dexamethasone dosing (i.e., loading failures and following discontinuation of the study drug).
- n) Video recording will not be required at the screening visit. The ICARS will be performed twice at Baseline, 24 hours apart (Days 0 and 1); the rating on Day 1 (pre-dose) will be used as the baseline value for statistical analyses. ICARS video recording will be required for both the Day 0 and Day 1 (baseline) assessments.
- o) For women of childbearing potential only. The test results must be negative at screening (serum) and baseline (urine) for the patient to be eligible for the study. Urine pregnancy test will be performed before every infusion.
- p) A Safety Follow-up assessment will be performed 30 days after the final evaluation or at least 60 days after the final infusion, whichever is longer; at this visit, the occurrence of any AEs or Serious AEs since the final evaluation will be reported.
- q) If the genetic test for AT has not been performed previously, the test will be done by the central laboratory. For patients who require genetic testing to confirm the diagnosis, test results do not need to be available before baseline.
- r) Patients originally randomized to placebo will be re-randomized to receive one of the two doses of EDS-EP, with one third of patients being switched at 6 months and another third at 9 months.
- s) Hemolysis panel: free plasma hemoglobin, haptoglobin, bilirubin (total and conjugated), CBC (Day 2 and 15 only), LDH, and urinalysis (Day 2 and 15 only). On Day 1, M3, M6 (b) and M9, only free plasma hemoglobin will be measured, 1 hr post-infusion.
- t) RBC osmotic resistance to be measured on a blood sample taken at screening and on a sample from the EryKit_01 bowl at the end of the process in selected centers only.

Version 1.0, 09May2015; Version 2.1, 16Nov2015; Version 3.0 (Amend. 1), 01Feb2016; Version 3.1 (Amend. 2), 28Apr2016; Version 3.2 (Amend. 3), 25May2016; Version 4.0 (Amend. 4), 29Nov2016; Version 5.0 (Amend. 5, Site-specific), 20Sep2017; Version 6.0 (Amend. 6), 29Sep2017; Version 7.1 (Amend. 7.1), Final 13 March 2018, Version 8.0 (Amend. 8.0), Final 23 April 2018; Version 10.0 (Amend. 10), Final 16 April 2019; Version 11.0 (Amend. 11), Final 24 Jun 2020

- u) Upon completion of the EDS process, the remaining sample in the satellite sample bag or, if this is not available, a sample collected from another EDS-EP sampling point, will be used for determination of DSP content and CBC.
- v) Patients meeting all selection criteria at Baseline will be randomized (1:1:1) to one of the three treatment groups.
- w) Blood sample for serum creatinine measurement to be taken before infusion.
- x) Vital signs to include height and weight measurements in triplicate at screening, baseline and each monthly visit (pre-dose).
- y) Month 12 (Visit 15; Endpoint) evaluations should be performed for all patients that complete the Extension Treatment Period, as well as patients that discontinue prematurely.
- z) The monthly infusions should be performed every 21-28 days. A window of ± 7 days will be permitted on the Day 15 visit and of + 10 days on each of the scheduled monthly post-baseline visits (Months 1 - 12). However, no EDS-EP infusion should be performed less than 21 days after the previous infusion. The window between an infusion and the subsequent one should be kept as regular as possible throughout the study, avoiding fluctuations in administration windows. The date of an infusion is not bound to the date of the initial treatment but to the date of the previous IMP administration. .
- aa) 1 mL blood collected, after blood diversion, for aerobic culture, before EDS process (see “Revised Study Procedures on Sterility Testing for Study IEDAT-02-2015 (ATTeST)”; [Appendix 13](#)). Moreover, a sample of the EDS-EP (approximately 1 ml per inoculum for a total of 2 mL) will be collected from the satellite sample bag to perform a culture-based sterility test. A 1-mL sterile sample of the EDS-EP will be stored under refrigeration as a "Retention Sample".
- (£) In case a patient is willing to be enrolled in the open-label study IEDAT-03-2018, but the study has not yet received IRB/EC approval at the time the patient reaches Visit 15/Month 12, the patient may undergo unscheduled monthly assessments/infusions (according to the assigned blinded treatment) starting from the time Visit 15/Month 12 should be performed, and continuing until the site has been initiated for the open-label study IEDAT-03-2018 and he/she has been evaluated for eligibility for the study. An additional Informed Consent Form must be signed prior to the 1st unscheduled visit/infusion.
- (§) As a results of the COVID-19 pandemic, temporary additional safety assessments may be requested at some visits. These changes are described in [Appendix 14](#).

Clinical Study Protocol IEDAT-02-2015

EDS in Ataxia Telangiectasia Patients

Version 1.0, 09May2015; Version 2.1, 16Nov2015; Version 3.0 (Amend. 1), 01Feb2016; Version 3.1 (Amend. 2), 28Apr2016; Version 3.2 (Amend. 3), 25May2016; Version 4.0 (Amend. 4), 29Nov2016; Version 5.0 (Amend. 5, Site-specific), 20Sep2017; Version 6.0 (Amend. 6), 29Sep2017; Version 7.1 (Amend. 7.1), Final 13 March 2018, Version 8.0 (Amend. 8.0), Final 23 April 2018; Version 10.0 (Amend. 10), Final 16 April 2019; Version 11.0 (Amend. 11), Final 24 Jun 2020

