--	---

	
treatment and country, comparing the two EDS dose ranges (~5-10 and~14-22 mg DSP/infusion) vs. placebo (as above).
 
The blind will be broken after all patients have completed the 6-month, double-blind, Initial Treatment Period, and the database for this period has been locked, so that the primary efficacy analysis can be performed. Therefore, procedures will be implemented to ensure that the blind is maintained for the 6-month, double-blind, Extension Treatment Period, so that the analyses of the data collected in this extension period are valid (See Section 16.2.8 for details).
 
Safety Analysis
 
All AEs will be summarized by body system and preferred term and treatment group. The incidence (%) of SAEs, AEs that are newly occurring or worsened after administration of study medication, and AEs leading to discontinuation (ADOs) will also be summarized. The intensity of AEs and relationship to the study medication, as assessed by the investigators, will also be presented. Results from vital signs, ECGs and laboratory tests, and physical and neurological examination findings will be summarized descriptively, with abnormal and clinically notable values/findings being identified. The change from baseline to endpoint in the C-SSRS will be analyzed using ANCOVA.
 
Data Safety Monitoring Board (DSMB)
 
An independent Data Safety Monitoring Board (DSMB) will review safety and tolerability data from the trial. The DSMB will receive unblinded safety data for review at specified intervals and will have the authority to modify or stop the trial if significant safety concerns are detected.
 
The DSMB will review all of the safety data on an ongoing basis, with special emphasis on the incidence and severity of steroid-related events, new infections, and serious AEs and deaths, in addition to the standard safety parameters
 
Pharmacokinetics (PK)
 
A population PK analysis will be performed for dexamethasone administered via EDS, based on the pooled data for dexamethasone plasma concentrations from all samples obtained from patients in each of the EDS treatment groups. In addition, for a sub-group of patients for which >80% of planned samples are collected after the first infusion (i.e. at least 5 of 6 post-dose samples are collected through Day 30 [Month 1]), the following PK parameters will be calculated for each patient, based on plasma levels of dexamethasone: C_{max}, t_{max}, AUC, apparent half-life. A mean, standard deviation, median, and range (minimum, maximum) for each of these parameters will be calculated and compared between the two dose groups for EDS.
 
Details of the planned PK analyses will be provided in a separate document.

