- Patients originally randomized to the Placebo group (Group 3) will be re-randomized (randomization to be done at baseline) in equal proportions (1:1) to receive either the EDS-EP ~5-10 mg DSP/ infusion or ~14-22 mg DSP/infusion (or the remaining dose of EDS-EP, if one of the doses has been eliminated following the Interim Analysis), as follows:
 - Following 6 months of treatment, one third of the placebo patients will be switched to treatment with EDS-EP, as described above;
 - After 9 months of treatment, one third of the placebo patients will be switched to treatment with EDS-EP, as described above;
- At 12 months, all remaining placebo patients who continue in the open-label phase will receive treatment with EDS-EP, as described above.

Visit 9 (Month 6) evaluations from the Initial Treatment Period will serve as the Baseline assessments for the Extension Treatment Period. Once these are completed, patients will have blood drawn for the EDS encapsulation procedure and will receive the infusion as before. Vital signs and a physical examination will be performed after dosing.

Subsequently in the Extension Treatment Period, EDS-EP infusions will be performed at Months 7, 8, 9, 10 and 11 (Visits 10 – 14), after which vital signs (including body weight and height in triplicate) and a physical examination will be performed. The C-SSRS assessment will also be performed at each of these visits. A blood sample will be collected for measurement of serum creatinine at Months 7, 8, 10 and 11, whereas creatinine will be part of the routine laboratory tests at Months 9 and 12. In addition, on Month 9 (Visit 12), all efficacy assessments (ICARS, CGI-C, CGI-S, VABS, and QoL) will be done prior to the infusion, and the neurological examination, routine laboratory tests and the ECG will be repeated. Upon completion of the EDS process 2.5 mL of the processed blood will be collected for measurement of DSP concentration and a CBC.

At Months 6 and 9, in selected centers, a 5-mL sample will be taken from the EryKit_01 bowl at the end of the process to assess RBC osmotic resistance. At Months 6 and 9, a hemolysis panel will be done pre- and post-infusion.

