14.6 Independent Data Safety Monitoring Board

An independent Data Safety Monitoring Board (DSMB) will be established by EryDel to review the safety of all patients enrolled in this trial, on an ongoing basis. No EryDel employee or investigator involved in the EDS clinical studies will be a voting member of this board. The DSMB will regularly review the safety data as it accrues.

The Board will be regularly notified of the occurrence of any fatal or life threatening events immediately (within 7 calendar days) and any other serious adverse events within 15 calendar days. The Board will also receive updates on any adverse dropouts on a regular basis (once per month). The Board will have access to the blinded safety data including serious AEs and adverse dropouts, as well as clinically significant abnormal laboratory tests, vital signs and ECGs at periodic intervals. The Board may request an unblinding of the treatment groups if there is a safety concern.

The DSMB will review all of the safety data on an ongoing basis, with special emphasis on the incidence and severity of steroid related events, new infections, and serious AEs and deaths, in addition to the standard safety parameters. After reviewing the emerging safety profile for EDS-EP, the Board will make a recommendation to EryDel to (a) amend the ongoing study (e.g., increase safety monitoring, modify dosing), (b) terminate the EDS program (e.g., the EDS-EP safety profile is unacceptable), (c) continue the clinical program as designed. The current study protocol will not be amended or changed (this includes the study design and entry criteria) unless mandated by the emerging (unblinded) safety profile of EDS-EP.

Details of the DSMB charter (separate document) will be submitted to regulatory authorities, and will be available to IECs/IRBs upon request.

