16.2.6.1 Interim Safety Analysis

An independent Data Safety Monitoring Board (DSMB) will be established by EryDel to review the safety of all patients enrolled in this trial, on an ongoing basis. No EryDel employee or investigator involved in the EDS-EP clinical studies will be a member of this board. The DSMB will periodically review the safety data accrued.

The DSMB will meet regularly to assess the safety from the emerging data. The first DSMB meeting will occur prior to the start of the trial, and the DSMB will decide when the first data review safety DSMB meeting will occur. They will also propose a tentative schedule for subsequent meetings that they may alter based on emerging safety data. The time between successive meetings should not be more than three months.

After reviewing the emerging safety profile for EDS-EP, the DSMB will make a recommendation to EryDel to (a) amend the ongoing EDS-EP study, (b) terminate the EDS-EP, or (c) continue the clinical program as designed. The current study will not be amended or changed (this includes the study design and entry criteria) unless mandated by the emerging (unblinded) safety profile of EDS-EP.

A separate DSMB Statistical Analysis Plan will be developed for specifying the analyses, tables, listings and figures to be prepared for DSMB meetings.

The DSMB will be regularly notified of the occurrence of any fatal or life threatening events immediately (within 7 calendar days) and any other serious adverse events within 15 calendar days. The DSMB will also receive updates on any adverse dropouts on a regular basis (once per month). The DSMB will have access to the blinded safety data including serious AEs and adverse dropouts, as well as clinically significant abnormal laboratory tests, vital signs and ECGs at periodic intervals. The DSMB may request an unblinding of the treatment groups if there is a safety concern.

Details of the DSMB charter (separate document) will be submitted to regulatory authorities, and will be available to Ethics Committees/IRBs upon request.

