5.9 Data Monitoring

An independent Data Safety Monitoring Board (DSMB) was established by EryDel to review the safety of all subjects enrolled in this trial, on an ongoing basis. No EryDel employee or investigator involved in the EDS-EP clinical studies is a member of this board. The DSMB periodically reviews the safety data accrued.

The DSMB met regularly to assess the safety from the emerging data. The first DSMB meeting was conducted prior to the start of the trial, and the DSMB decided when the first data review safety DSMB meeting would occur. DSMB meetings were held when 9 patients completed 30 days of treatment. In January 2020, the DSMB agreed to quarterly meetings.

The DSMB will be regularly notified of the occurrence of any fatal or life-threatening events within 7 calendar days and any other serious adverse events within 15 calendar days. The DSMB will also receive updates on any adverse dropouts on a regular basis (once per month). The DSMB will have access to the blinded safety data including serious AEs and adverse dropouts, as well as clinically significant abnormal laboratory tests, vital signs, and ECGs at periodic intervals. The DSMB may request an unblinding of the treatment groups if there is a safety concern.

The DSMB will review all of the safety data on an ongoing basis, with special emphasis on the incidence and severity of steroid related events, new infections, and serious AEs and deaths, in addition to the standard safety parameters. The Board will make a recommendation to EryDel to (a) amend the ongoing study (e.g., increase safety monitoring), (b) terminate the EDS program (e.g., the EDS-EP safety profile is unacceptable), or (c) continue the clinical program as designed. The current study protocol will not be amended or changed (this includes the study design and entry criteria) unless mandated by the emerging (unblinded) safety profile of EDS-EP.

Details of the DSMB charter (separate document) will be submitted to regulatory authorities and will be available to Ethics Committees/IRBs upon request.

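### The synopsis gives the DSMB unblinded data and power to stop the trial, while the protocol body and SAP give it blinded data and an advisory role, so routine comparison of arms is not assured

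*Protocol*

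**What the plan says.** The DSMB is described in four places.

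- **Protocol synopsis, Statistical Methods:** "The DSMB will receive unblinded safety data for review at specified intervals". The board may itself modify or stop the trial if significant safety concerns are found.
- **Protocol 14.6:** "The Board will have access to the blinded safety data including serious AEs and adverse dropouts". It adds: "The Board may request an unblinding of the treatment groups if there is a safety concern". After its review the board makes a recommendation to the sponsor.
- **Protocol 16.2.6.1:** "The DSMB will have access to the blinded safety data including serious AEs and adverse dropouts", with the same request route and the same advisory role. A separate DSMB statistical analysis plan will specify the tables, and a charter is also a separate document.
- **SAP 5.9:** again blinded data and a recommendation, and "The DSMB may request an unblinding of the treatment groups if there is a safety concern".

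The synopsis, protocol 14.6 and SAP 5.9 share a stated focus. In the words of 14.6, the review is carried out "with special emphasis on the incidence and severity of steroid related events, new infections, and serious AEs and deaths".

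Protocol 14.6, protocol 16.2.6.1 and SAP 5.9 each say the study will not be changed "unless mandated by the emerging (unblinded) safety profile of EDS-EP". Protocol 11.2 provides for the case "if one of the doses has been eliminated following the Interim Analysis", and SAP 5.8 explains that this means interim safety analyses and DSMB actions, not an interim efficacy analysis.

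**The concern.** The board's main task is to judge whether either of two dexamethasone dose ranges causes harm relative to placebo. That judgement needs data by arm, and it is harder without them in this trial than in most:

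- **High background risk.** Protocol 7.3 gives increased susceptibility to chronic nasal and pulmonary infections in 70% of patients with ataxia telangiectasia, so infections are expected in every arm.
- **No placebo reference from the earlier study.** The phase II study in this disease was single-arm and open-label (protocol 7.1.3.1). In it, 2 of 22 patients had falls in CD4+ count of more than 20% that were considered related to study medication and led to discontinuation.
- **Changing exposure.** In the extension, placebo patients move to active treatment at Months 6 and 9, so the mix of treatments shifts over time.

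If the synopsis governs, the board sees the arms at every review. If the body and SAP govern, it does so only after it has become concerned for some other reason. The same four places also disagree on whether the board acts or advises, which matters most at the moment a safety signal appears.

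**Working it through.** No arithmetic applies. The check is to set the passages side by side.

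**Step 1. What the board sees and may do.**

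| Place | Data supplied | Route to unblinding | Power |
|---|---|---|---|
| Protocol synopsis | Unblinded, at specified intervals | None needed | Authority to modify or stop |
| Protocol 14.6 | Blinded, at periodic intervals | On request, if there is a safety concern | Recommendation to sponsor |
| Protocol 16.2.6.1 | Blinded, at periodic intervals | On request, if there is a safety concern | Recommendation to sponsor |
| SAP 5.9 | Blinded, at periodic intervals | On request, if there is a safety concern | Recommendation to sponsor |

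One statement of four differs from the other three in every column. All four are current text; no redaction or amendment log accounts for the difference.

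**Step 2. Consistency within the three blinded sections.** Each makes any change depend on an unblinded profile ("unless mandated by the emerging (unblinded) safety profile of EDS-EP") while supplying blinded data by default. The basis for action is not what the board routinely receives.

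**Step 3. Consistency with the dose-elimination text.** Protocol 11.2, read with SAP 5.8, foresees one dose being dropped after interim safety review. Choosing between two doses on safety grounds needs data by arm at some point. Protocol 14.6 likewise gives modified dosing as an example of an amendment the board might recommend. Neither fits a default of blinded data.

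**Step 4. The trigger.** Under 14.6, 16.2.6.1 and SAP 5.9 the sequence is blinded data, then a concern, then a request, then data by arm. An imbalance between arms is the usual reason for concern about a dose-related effect, but here it can be seen reliably only after the request, unless blinded reports already separate the arms under codes.

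**Step 5. What is left open.** None of the four places defines blinded (arms combined, or arms under masked codes), says to whom an unblinding request goes or who grants it, or says who prepares the board's tables. SAP 5.8 describes an unblinded second biostatistics team, but for the primary efficacy analysis, not for the DSMB.

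**The case against.** The strongest reply has four parts.

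**The board is not shut out.** A reader might infer that, as written, it cannot compare arms at all. The documents do not support that. Three sections let it request unblinding and set no threshold, so the board judges what counts as a concern. It hears of fatal or life-threatening events within 7 days, other serious events within 15 days and adverse dropouts monthly, so a concern can arise from individual cases. This stands. It limits the point to routine comparison, but does not help with a moderate excess of common events such as infections, where no single case is striking.

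**Blinded need not mean combined.** A reader might also infer that the board sees only data with the arms merged. No passage says so; tables under masked arm codes could be called blinded and would allow comparison. This stands too, and is a reason to define the term.

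**The operational documents may settle it.** The DSMB analysis plan and charter were not available, so what the board actually received cannot be determined. But neither document can agree with both the synopsis and the other three sections. Whichever it follows, some text reviewed by regulators and ethics committees is wrong.

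**It is late.** Enrollment closed in March 2020, and SAP 5.9 describes DSMB activity partly in the past tense, with quarterly meetings agreed in January 2020. This bears on cost, not on whether the texts conflict.

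**Conclusion.** The contradiction holds, on two counts: unblinded against blinded data, and authority to act against a power to recommend. A further tension lies within protocol 14.6, protocol 16.2.6.1 and SAP 5.9, and between them and the dose-elimination text in protocol 11.2 and SAP 5.8. The supported consequence is that routine comparison of arms for steroid-related events, infections, serious adverse events and deaths is not assured under the body and SAP text. This rests on reading blinded as possibly, not necessarily, without separation of arms, and on the protocol and SAP alone.

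The size cannot be put as a number: the documents give no event rates by arm, and any illustration would rest on invented ones. Type I error, power and sample size are unaffected. The point concerns safety oversight and should be corrected.

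**What to change.** 1. Reconcile the synopsis with protocol 14.6 and 16.2.6.1 and SAP 5.9, so that each scheduled DSMB meeting receives closed safety tables by coded or labelled arm, prepared by a statistician independent of the blinded study team.
2. Define blinded wherever it is used for DSMB data. If an unblinding request remains possible, say who receives and grants it.
3. State one rule, in all four places, on whether the board decides or recommends.
4. Reconcile protocol 11.2 and SAP 5.8 with the same text, so that the data needed for any DSMB action on a dose are the data the board is said to receive.
5. Align the charter and the DSMB analysis plan. If they already provide tables by coded arm, the remaining work is to correct the protocol and SAP wording.

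The cost is an amendment to protocol and SAP wording, which under protocol 17.2 needs ethics committee approval unless it is administrative, across the planned 20-25 centers. Access to closed reports must also be controlled so that sponsor, sites and raters stay blinded. Randomization, visits, endpoints and the efficacy analysis do not change.
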